## A. Introduction and Background

People who inject drugs (PWIDs) are a socially vulnerable population and are exposed to risk factors including unstable housing and underlying medical conditions such as human immunodeficiency virus (HIV), tuberculosis (TB), and viral hepatitis that put them at increased risk for severe COVID-19 symptoms, including death. PWIDs also experience barriers such as a history of stigmatization and discrimination by health care systems and exposure to misinformation about testing that reduces access to health care services and testing. Because timely receipt of services relative to symptoms onset is critical for positive health outcomes and to reduce SARS-CoV-2 transmission, lack of testing has significant implications for PWID, highlighting an urgent need to increase testing uptake among this population. Despite this, PWIDs have been an underserved population in the context of the current pandemic; thus, little is known about the prevalence of COVID-19 and the acceptability and possible reach of testing for COVID-19 among PWIDs. To address this gap, this study leverages a current partnership with HIV Alliance (HIVA) in Oregon and our Community and Scientific Advisory Board to support implementation and sustainability of a COVID-19 testing program. Specifically, we will use community-based participatory approaches to develop, implement, and evaluate a COVID-19 testing program offered through HIVA's Syringe Services Programs (SSP), a natural point of care for PWIDs. Moreover, SSPs may offer a natural venue for dissemination and delivery of a vaccine, once available. The COVID-19 testing program will include procedures for sample collection, transmission of specimens to the University of Oregon CLIA-certified laboratory, and results reporting. For aim 1, we will assess the testing program utilization. For aim 2, we will develop and test a brief motivational enhancement intervention to optimize testing utilization among PWIDs. Using a randomized control trial design, we will evaluate intervention effects on utilization of COVID-19 testing resources. For aim 3, we will collect data from syringe exchange staff and key volunteers on program acceptability, feasibility, appropriateness, adoption, and implementation barriers and facilitators related to the testing program and intervention. The current project has the potential to enhance COVID-19 testing access and reach among a significantly underserved population who experience multiple risks that make it difficult to prevent SARS-CoV-2 exposure and transmission and who are at increased risk for severe COVID-19 symptoms, if they were to contract the disease.

## B. Specific Aims/Study Objectives

We will accomplish our goals to increase testing capacity and utilization of testing resources for PWIDs by accomplishing the following specific aims:

**Aim 1:** Use a community-based participatory approach to collaborate with HIVA to build their capacity to implement a sustainable COVID-19 testing program that will include procedures for sample collection, transmission of specimens to the University of Oregon CLIA-certified laboratory, and results reporting, and assess testing utilization to understand the reach of the program.

**Aim 2:** Develop a brief one-session intervention (i.e., Connect2Test) that incorporates ecological assessment and motivational interviewing and that can be implemented during syringe exchange services. We will use a randomized control trial design to evaluate whether the Connect2Test intervention increases the likelihood of COVID-19 testing and retesting in comparison to a control condition. We will also test whether social determinants of health (SDOH) linked to COVID-19 moderate intervention effects.

**Aim 3:** Assess implementation outcomes associated with COVID-19 testing and the Connect2Test intervention. We will collect qualitative and quantitative data from HIVA staff and key volunteers to examine acceptability, appropriateness, feasibility, adoption, and sustainability of the testing program and

Connect2Test intervention and identify implementation barriers and facilitators that can be used to adapt the testing and Connect2Test for scale-up.

## C. Methods, Materials and Analysis

Overall Study Design: This study involves development and implementation of a COVID-19 testing program embedded in HIV Alliance's (HIVA) Syringe Service Programs (SSP) at 10 sites across Oregon (Aim 1). We will evaluate testing utilization rates as our outcome for Aim 1. Across all sites, for Aim 1, we expect to offer testing to 3800 unique individuals in Year One and to administer approximately 150 tests per week. For Aim 1, we will compute the ratio of total persons tested/total persons attending syringe exchange who were offered testing (n=3800) to assess testing program reach. The UO COVID-19 MAP laboratory will report number of tests collected per site per week and HIV Alliance will share the number of individuals served per site per week. For Aim 1, HIVA SSP clients will also be invited to complete a "Common Data Elements" survey for the funder, National Institutes of Health. No identifying information is collected on the "Common Data Elements" survey. At the time of testing, the HIVA testing facilitator will invite clients to complete the survey and obtain signed informed consent. Consents and surveys will be read by the clients and completed via paper-pencil. Clients who complete the survey will receive a \$10 gift card for their participation.

For Aim 2, we will develop a brief motivational enhancement intervention (Connect2Test) to increase testing program utilization and use a randomized control trial (RCT) design to evaluate if this intervention increases COVID-19 testing utilization, in comparison to a control condition. While the testing program will be implemented in 10 HIVA sites for Aim 1 to assess reach of the testing program, the RCT in Aim 2 will be limited to the six syringe exchange sites in Lane County to limit travel. Following client participation in syringe exchange services, clients will be invited to participate in the RCT by the research team member on site. Clients that agree to participate will complete signed informed consent programmed in Qualtrics and consented participants will be randomized to the intervention or control condition by Qualtrics. At the time of consent, research staff will ask clients to complete a HIPAA Authorization form for the purpose of sharing their testing utilization data with the UO research team. The HIPAA Authorization form will also be programmed in Qualtrics. All participants, regardless of randomization, will complete a study questionnaire (in Qualtrics) that includes both the Connect2Test Assessment questions and Common Data Elements questions. For clients randomized to the intervention, the Connect2Test Assessment questions will be used to guide the Connect2Test motivational interviewing intervention component. Clients in the control condition will be invited to participate in testing after completing the survey. Clients in the intervention condition will be invited to participate in testing after the motivational interviewing intervention component. Clients who agree to participate in the RCT will receive a \$20 gift card. The target sample size for the RCT in Aim 2 is 250 unique individuals. The RCT will be initiated approximately 2 months after the testing program has been initiated and we anticipate it will take approximately 1 month to reach the target sample size.

For Aim 3, we will collect survey and interview data on implementation experiences from HIVA staff and volunteers.

The research will occur at HIVA SSP sites across the state of Oregon. HIVA will be responsible for coordinating training activities for HIVA staff and UO will be responsible for training HIVA staff on-site and virtually. HIVA will meet with the UO implementation team ([name], [name], [name]) at least monthly (but more frequently to start).

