### Research Procedures:

**Testing Program: Aim 1.** The UO COVID-19 MAP laboratory will report number of tests collected per site per week and HIV Alliance will share the number of individuals served per site per week. HIVA SSP clients will also be invited to complete a "Common Data Elements" survey for the funder, National Institutes of Health. No identifying information is collected on the "Common Data Elements" survey. At the time of testing, the HIVA testing facilitator will invite clients to complete the survey and obtain signed informed consent. Consents and surveys will be read by the clients and completed via paper-pencil. If clients cannot read, the survey may be read to them. If the survey is read aloud, it will be done in a space away from other clients to maintain privacy. Clients who complete the survey will receive a \$10 gift card for their participation.

Any client can receive COVID-19 testing, regardless of their participation in the research.

**Connect2Test Evaluation: Aim 2:** We will use community-based participatory approaches to develop a brief one-session intervention that will include an ecological assessment, feedback, and motivational interviewing, called Connect2test. While Connect2Test draws from principles used in the Family Check-Up, such as ecological assessment, feedback, and motivational interviewing, the Connect2test intervention is unique from the Family Check-Up. We will use a randomized control trial (RCT) design to evaluate if Connect2test increases COVID-19 testing utilization, in comparison to a control condition. The RCT in Aim 2 will be conducted at the six syringe exchange sites in Lane County.

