#### **D. Research Population & Recruitment Methods**

**Study Population:** The study population will be people who inject drugs (PWID) and use HIVA's SSP services in Oregon. We anticipate the sample characteristics to be comparable to demographics for individuals who typically participate in syringe exchange. Specifically, we expect 6% Hispanic and 94% non-Hispanic, with 85% of individuals identifying as White in both ethnic groups and the remaining 15% identifying as African American, Asian, Pacific Islander, American Indian/Alaska Native, or more than one race. Only individuals 18 and older will be eligible to participate in testing and the intervention study. All study and intervention materials will be available in English. Although all participants regardless of language spoken will be invited to test, only participants who speak English will be eligible for the RCT (Aim 2), as Connect2Test materials will only be available in English. We anticipate approximately 3800 unique participants will be included in Aim 1 and approximately 250 unique participants will be included in Aim 2. All HIVA SSP clients (up to testing capacity, i.e., 150 per week) will have access to and be invited to test. We expect an excess of male participants (i.e., 60%), based on the demographics of persons who use syringe exchange services. Across all sites, we expect to offer testing to 3800 unique individuals in Year One and to administer approximately 150 tests per week.

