**Recruitment Procedures:**

**For Aim 1**, data from all syringe exchange service participants across 10 HIVA syringe exchange sites will be included in this study. HIVA SSP clients will also be invited to complete a "Common Data Elements" survey for the funder, National Institutes of Health. No identifying information is collected on the "Common Data Elements" survey. At the time of testing, the HIVA testing facilitator will invite clients to complete the survey and obtain signed informed consent. Consents and surveys will be read by the clients and completed via paper-pencil. In most cases, clients will self-administer the survey but if they cannot read, the survey may be read to them. If the survey is read aloud, it will be done in a space away from other clients to maintain privacy. Clients who complete the survey will receive a \$10 gift card for their participation.

**For Aim 2**, a research staff person will invite syringe exchange service participants to participate in the study when they visit the exchange for services (see Recruitment script). The research staff will inform clients about the opportunity to participate in the research study and obtain signed informed consent. At the time of consent, research staff will ask clients to complete a HIPAA Authorization form for the purpose of releasing their testing utilization data to the UO research team. The HIPAA form will also be programmed in Qualtrics. UO's COVID-19 MAP will only give the research team access to testing utilization data for HIVA IDs for whom we have a HIPAA authorization and consent. Clients will be given a blank consent and HIPAA form. During the course of the RCT, clients will only be invited to participate in the study once. Research staff will document participation to target recruitment of unique individuals visiting the exchange. Regardless of whether clients consent to participate in the study, they will be offered an opportunity to get tested every time they visit the exchange. The RCT in Aim 2 will be conducted at the six syringe exchange sites in Lane county; participants will be recruited from these six sites.

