## E. Informed Consent Process

**Aim 1.** To assess the Aim 1 outcome, proportion of HIVA syringe exchange clients being tested, no individual level data is being collected by the research team. We will compute proportions based on aggregate weekly syringe exchange and testing data. At the time of testing, the HIVA testing facilitator will invite clients to complete the Common Data Elements survey and obtain signed informed consent. No identifying information is collected on the “Common Data Elements” survey. Consents and surveys will be read by the clients and completed via paper-pencil. If clients cannot read, the survey may be read to them. If the survey is read aloud, it will be done in a space away from other clients to maintain privacy. Clients who complete the survey will receive a \$10 gift card for their participation.

**Aim 2:** Clients attending the syringe exchange will be invited to participate in the RCT by a research staff. Clients who agree to participate will provide signed informed consent via Qualtrics, and participants that consent will be randomized to the intervention or control condition via Qualtrics. At the time of consent, the research staff will review the consent with the participant before they sign it to ensure that the participant is clear about data will be obtained by National Institutes of Health and Duke Clinical Research Institute versus the UO. The research staff will also clarify that the identifying information that the participant includes in the CDE survey will be used by National Institutes of Health (NIH) and Duke Clinical Research Institute (DCRI) to link to other data such as Medicaid data, though once linked the data will be de-identified. The research assistant will also clarify that Medicaid and other data to which NIH/DCRI links will not be used by UO.

Participants who participate will receive a \$20 gift card. At the time of consent, the research team member will ask clients to complete a HIPAA Authorization form (also in Qualtrics) for the purpose of releasing their testing utilization data to the UO research team. UO's COVID-19 MAP will only give the research team access to testing data for people for whom we have a HIPAA authorization and consent. Clients will be given a blank paper copy consent and HIPAA form.

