### 2. Data Disposition

For Aim 1, no identifying data will be linked to CDE survey data. Specifically, data will be entered using the HIVA ID only. For Aim 1 outcome, no individual level testing data is being collected by the research team. The CDE survey data is individual level data.

For aim 2, consents and HIPAA Authorization are programmed with the survey questions but identifying information (names on consent/HIPAA) will be stripped from the data at earliest opportunity. All data will be retained and stored for the duration of record storage but will be de-identified with a “code key” following study completion by assigning a new ID to the data. This code key will be kept separate from the data and the de-identified data on the secure file server at the Prevention Science Institute. Data will be maintained by the research study team. Data will be transmitted between the research team and UO COVID-19 MAP lab and

between the research team and HIVA using encrypted, secure email. Data will only be transmitted for participants for whom the research team has consent and HIPAA authorization for sharing of testing data.

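### Aim 1 reach is defined as persons tested over persons offered testing, but the weekly site counts named as its inputs cannot give that ratio

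*Protocol*

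**What the plan says.** Section C (Overall Study Design) defines the Aim 1 outcome in persons: "we will compute the ratio of total persons tested/total persons attending syringe exchange who were offered testing (n=3800) to assess testing program reach". The same paragraph gives the planning figures: "we expect to offer testing to 3800 unique individuals in Year One and to administer approximately 150 tests per week".

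The inputs are named in Section C and again under Research Procedures (Testing Program: Aim 1). The University of Oregon laboratory "will report number of tests collected per site per week and HIV Alliance will share the number of individuals served per site per week".

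Section E (Informed Consent Process, Aim 1) describes the outcome as the "proportion of HIVA syringe exchange clients being tested, no individual level data is being collected by the research team", and adds: "We will compute proportions based on aggregate weekly syringe exchange and testing data". Section F.2 (Data Disposition) agrees: "For Aim 1 outcome, no individual level testing data is being collected by the research team".

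Two passages bear on who is in the denominator. Section D (Recruitment Procedures) says "data from all syringe exchange service participants across 10 HIVA syringe exchange sites will be included in this study". Section D (Study Population) says "All HIVA SSP clients (up to testing capacity, i.e., 150 per week) will have access to and be invited to test".

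The Aim 2 text under Research Procedures notes that the HIVA ID links the records of people who use the services repeatedly.

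**The concern.** The outcome is a proportion of people, but the planned data are counts of tests and of individuals seen in a given site and week. Two steps are missing between them. Nothing turns tests into persons with at least one test. Nothing turns weekly site counts into unique persons over the year, although the protocol recognises that clients return.

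Section B gives understanding the programme's reach as the reason for assessing utilisation in Aim 1. Testing many clients once and testing a few clients many times are opposite findings about reach. If only the named counts are collected, the two look the same, and no later analysis of those counts can separate them.

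**Working it through.** **Inputs from the protocol.** 3800 unique individuals expected to be offered testing in Year One and about 150 tests per week (Section C). The 150 is also called a capacity (Section D, Study Population). The protocol states no expected reach and no number of testing weeks, so there is no result of its own to reproduce.

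**Assumed quantities, not in the protocol.** Let *T* be total tests, *N* the number of unique clients offered testing, *m* the mean tests per tested person, and *v* the mean number of weeks attended per client. For the illustration every client served is taken to have been offered testing, and each client is counted once in each week attended.

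**What the two quantities are.**
- Reach as defined = persons tested / persons offered = (*T*/*m*)/*N*.
- Ratio available from the weekly counts = *T*/(*N* × *v*), because weekly individuals served add up to person-weeks.
- Hence weekly ratio = reach × *m*/*v*. The two agree only when *m* = *v*, and the named counts supply neither.

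**Numerator.** Take *T* = 3,000 and *N* = 3800:
- *m* = 1: 3,000 persons tested; 3,000/3800 = 0.789, or 79%.
- *m* = 2: 1,500 persons tested; 1,500/3800 = 0.395, reported as 39%.
- *m* = 4: 750 persons tested; 750/3800 = 0.197, or 20%.

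If clients attend *v* = 4 weeks each, the served counts sum to 3800 × 4 = 15,200. The weekly ratio is then 3,000/15,200 = 0.197 in all three cases. One set of counts fits all three values of reach.

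**Denominator.** A served total of 15,200 could come from 3800 clients at four weeks each (15,200/4) or from 3,040 at five (15,200/5). The observed number of unique clients cannot be read from the weekly counts either.

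**When repeats become certain.** At 150 tests per week the test count reaches 3800 at 3800/150 = 25.3 weeks. At 25 weeks it is 150 × 25 = 3,750; at 26 weeks it is 150 × 26 = 3,900. If that rate were held for longer than about 25 weeks among 3800 people, some tests would have to be repeats, and tests divided by 3800 would exceed 1. Before that point repeats are possible but not forced.

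**The case against.** The strongest reply is that nothing forbids de-duplication. Sections E and F.2 restrict what the research team collects; HIVA or the laboratory could remove repeats by HIVA ID and send totals. That stands as a route to a solution. But the protocol does not say this will be done, and Section E names weekly aggregates as the basis of the calculation. An analysis plan could not repair it without different inputs.

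A second reply is that weekly utilisation was meant all along, since Section C introduces the Aim 1 outcome as utilisation rates. Weekly tests over individuals served is a sensible measure of that. The person-based ratio in the same paragraph would then be the wrong definition, so the text still needs correcting.

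A third is that Aim 1 survey data are entered under the HIVA ID (Section F.2) and the survey is offered at testing. This shows that IDs are in use in Aim 1. The survey is voluntary, however, and is not named as a source for reach, so its completers would at best give a lower bound on persons tested.

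A reader might also infer more than the documents support:
- *That invitations are capped, so served certainly differs from offered.* The capacity remark in Section D can equally be read as a limit on tests performed. It is unclear, and the protocol should say which is meant. If invitations were capped at 150 per week, the 3,000-test illustration would need a smaller denominator.
- *That 3800 will be used as a fixed denominator.* It reads naturally as the expected size of the group offered testing.
- *That the plan's own figures prove repeat testing.* They do so only beyond about 25 weeks at the full rate. Duration is not stated, and 150 is also a capacity. The text about offering tests at every visit, and about retesting, belongs to Aim 2.

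**Conclusion.** The point holds. The protocol defines reach in unique persons and limits its inputs to weekly counts of tests and of individuals served. Following the plan as written yields tests per person-week served, not the proportion of persons reached.

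The size of the error cannot be fixed from the documents, because it depends on tests per tester and weeks attended, and neither is given. The range of 79% to 20% is an illustration that rests on an assumed 3,000 tests, 3800 clients all offered testing, and one to four tests per tester. The mismatch itself does not depend on those values.

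This should be fixed because it decides what Aim 1 can conclude. The consequence is confined to that descriptive outcome. The Aim 2 randomised comparison uses individual yes/no utilisation linked by HIVA ID and is unaffected.

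**What to change.** Ask the laboratory and HIVA to send aggregate totals, de-duplicated by HIVA ID across all ten sites over one stated period:
- persons with at least one test;
- persons offered testing, or persons served if offers are not recorded, with a statement of which is used.

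Define reach as the first total over the second, using the observed values. Report weekly tests per individual served separately, as uptake. State whether the capacity of 150 per week limits invitations or tests.

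Confirm first that laboratory records carry a HIVA ID for every Aim 1 tester. The protocol shows such IDs for Aim 1 survey data and for laboratory data on consented trial participants, but does not say that they cover all testers. If they do not, relabel the outcome as tests per individual served per week and do not describe it as the proportion of persons reached.

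Bring Section C (Overall Study Design), Research Procedures (Aim 1), Section E (Aim 1) and Section F.2 into line with one definition and one set of inputs.

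The cost is some de-duplication work at the laboratory and HIVA. No additional participants are needed, and the research team would still receive only aggregates for this outcome. The fallback costs only a change of wording, at the price of giving up a statement about the proportion of persons reached.

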Following client participation in syringe exchange services, clients will be invited to participate in the RCT by a research staff. Clients that agree to participate will complete signed informed consent programmed in Qualtrics and consented participants will be randomized to the intervention or control condition by Qualtrics. All participants will complete a study questionnaire (in Qualtrics) that includes both the Connect2Test Assessment questions and Common Data Elements questions. For clients randomized to the intervention, the Connect2Test Assessment questions will be used to guide the Connect2Test motivational interviewing intervention component. The consent and all surveys/assessments will be administered via an iPad. Participants who participate in the study will receive a \$20 gift card. Recruitment script and consent are included with protocol. In most cases, clients will self-administer the survey; however, if they cannot read, the survey may be read to them. If the survey is read aloud, it will be done in a space away from other clients to maintain privacy. In total, surveys/assessment should take approximately 15 minutes to complete. Participants will receive a blank paper copy of the consent. Clients randomized to the intervention condition will participate in the Connect2Test motivational interviewing intervention component, which should take approximately 5 minutes. The motivational interviewing intervention component, which will be offered by a clinician on the research team, will be facilitated by a personalized feedback form that summarizes Connect2Test assessment data and that is auto-generated on the iPad that the client used to complete the Connect2Test assessment. After completing the motivational interviewing intervention component with the research team member, clients will be offered COVID-19 testing. Clients in the control condition will be invited to participate in testing after completing the survey. A research team member will assess Connect2Test fidelity on a randomly selected 20% of testing days. The clinician offering the intervention will also self-report on fidelity. We will use testing utilization (yes/no) as our outcome to evaluate intervention effects. Data from the CDE survey and the HIVA intake form will be leveraged to evaluate moderators of intervention effects.

Any client can receive COVID-19 testing, regardless of their participation in the research.

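### As the protocol reads, Aim 2 participants are randomised before the 15-minute questionnaire, although nothing differs by arm until it is finished; allocating after the last item would be a cheap improvement

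*Protocol*

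**What the plan says.** Protocol section C describes the Aim 2 flow twice. The overview of the design says that "consented participants will be randomized to the intervention or control condition by Qualtrics", and goes on: "All participants, regardless of randomization, will complete a study questionnaire (in Qualtrics) that includes both the Connect2Test Assessment questions and Common Data Elements questions". The Aim 2 text under Research Procedures puts the two steps next to each other in the same order: "consented participants will be randomized to the intervention or control condition by Qualtrics. All participants will complete a study questionnaire (in Qualtrics"). It also gives the length: "In total, surveys/assessment should take approximately 15 minutes to complete".

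The arms separate only after that. For controls, "Clients in the control condition will be invited to participate in testing after completing the survey". For the other arm, "Clients in the intervention condition will be invited to participate in testing after the motivational interviewing intervention component". The interview is built around a feedback form that the iPad generates from the client's Connect2Test Assessment answers.

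Section E (Informed Consent Process, Aim 2) ties allocation to consent: "participants that consent will be randomized to the intervention or control condition via Qualtrics". It does not say when the questionnaire is completed.

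Mediation of the effect is not at issue; moderation is. On the social determinants of health (SDOH) as moderators, Research Procedures says: "Data from the CDE survey and the HIVA intake form will be leveraged to evaluate moderators of intervention effects". The outcome is testing utilization (yes/no) from the laboratory, linked by HIVA ID and released to the research team where consent and HIPAA authorization exist.

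**The concern.** A moderator should be fixed before allocation. If it is recorded afterwards, and the client or the staff member already knows the arm, then answers or completion may differ by arm. The interaction test cannot separate that from true effect modification. Testing moderation by SDOH is part of Aim 2, so this touches a stated objective.

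The second matter is break-off. The survey comes after the client has already received exchange services, and some clients may leave before the end. Under the order described, they are already in the trial. An intervention client without a completed assessment lacks the material for the feedback form, and so counts in the intervention arm without having had the session as designed. Counting such clients as randomised is correct, but it pulls the two arms together.

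Both costs would be worth bearing if early allocation bought something. The protocol's flow shows nothing that it buys.

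**Working it through.** **Order of steps.** The text was checked place by place.

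| Place in protocol | What it fixes |
|---|---|
| Section C, overview of Aim 2 | Consent, randomisation, questionnaire for everyone whatever the arm, then arm-specific steps |
| Section C, Research Procedures, Aim 2 | Same order; survey about 15 minutes; feedback form made from assessment answers |
| Section C, Research Procedures, linkage and Data Analysis | Outcome from laboratory data; release needs consent and HIPAA authorization, not a finished survey |
| Section E, Aim 2 | Randomisation tied to consent; silent on the questionnaire |

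No section places allocation after the questionnaire, and none says when the arm is revealed. No arm-specific step precedes the last question.

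**Which moderators are affected.** Two sources are named. CDE items sit inside the questionnaire and so follow allocation. HIVA intake items are not part of it, and the protocol does not date them. Only the first group is affected.

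**Size of the dilution.** The only relevant figure in the document is the target of 250. It cannot be reproduced, because no alpha, power, testing rate, effect, allocation ratio or drop-out is given. The following is an illustration on assumed inputs:

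- 1:1 allocation, so n = 125 per arm; two-sided alpha 0.05 (z = 1.96)
- testing rates pC = 0.30 and pT = 0.47
- break-off d = 5, 10 or 20%, equal in both arms
- intervention clients who break off get no session and test at the control rate

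Power = Φ[(|pT − pC| − 1.96·SE0)/SE1], where SE0 = √(2·p̄(1 − p̄)/n), SE1 = √((pC(1 − pC) + pT(1 − pT))/n), and p̄ is the mean of the two rates.

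*No break-off:* SE0 = 0.0615, SE1 = 0.0606; (0.17 − 0.1206)/0.0606 = 0.81; power 0.79.

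*Early allocation, everyone analysed:* the intervention rate becomes (1 − d)·0.47 + d·0.30. At d = 10% this is 0.423 + 0.030 = 0.453, so the difference is 0.153. Then (0.153 − 0.1201)/0.0605 = 0.54; power 0.71.

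*Late allocation, same clients approached:* n falls to 125·(1 − d), and the rates stay at 0.30 and 0.47. At d = 10%, n = 112, SE0 = 0.0650, SE1 = 0.0640; (0.17 − 0.1274)/0.0640 = 0.66; power 0.75.

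| Break-off | Early: intervention rate | Early: power | Late: n per arm | Late: power | Late, recruiting on to 250 completers: power | Clients to consent, 250/(1 − d) |
|---|---|---|---|---|---|---|
| 5% | 0.4615 | 0.75 | 119 | 0.77 | 0.79 | 264 |
| 10% | 0.453 | 0.71 | 112 | 0.75 | 0.79 | 278 |
| 20% | 0.436 | 0.61 | 100 | 0.70 | 0.79 | 313 |

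With the same clients approached, late allocation gains about 2, 4 and 9 percentage points of power. It is the better order at each rate tried, even without replacing the losses.

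The early-allocation column is a worst case in one respect. The feedback form uses the Connect2Test Assessment only, and the order of the items is not stated. A client who finishes those items but leaves during the CDE items could still have the session.

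**The case against.** The strongest reply is that the order is read from narrative, and that the narrative is not strictly chronological. In sections C and E, steps that belong to the moment of consent are described after the sentence on randomisation. Saying that consented participants are randomised states who is allocated and need not fix where in the survey flow. This stands as a caution: the sponsor may already allocate later in practice. But both descriptions in section C read most naturally as allocation first, and no text says otherwise.

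A reader might infer that the moderator data are biased. The protocol does not support that. The questionnaire is identical in both arms, precedes the interview and is usually self-administered. Reading aloud is an option for clients who cannot read. Answers can be affected only if the arm is revealed early, and the protocol neither says that it is nor that it is hidden. A measure taken after a concealed allocation and before treatment is, in effect, a baseline measure.

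A reader might also infer that the main comparison is compromised. It is not. The outcome comes from the laboratory, and its release does not require a finished survey, so everyone randomised with consent and authorization can be analysed. An analysis of survey completers would lose the protection of randomisation, but the protocol proposes none.

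Finally, the break-off rates and the effect are assumed, and the dilution is modest. It would also be too much to say that the change costs nothing: the protocol does not discuss what Qualtrics can do, and later allocation needs more consents. These points limit the size of the concern. None of them gives a reason to allocate before the questionnaire.

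**Conclusion.** The point holds as an avoidable weakness in the order of steps. It is neither a contradiction nor an invalid comparison. As section C reads, allocation precedes a questionnaire that is common to both arms. The CDE-based moderators therefore lose their clear status as baseline measures, and clients who break off are kept in the randomised set. Moderators from the HIVA intake form are not part of this.

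Under the assumed 30% versus 47% and 125 per arm, early allocation costs about 2 to 9 percentage points of power at 5 to 20% break-off, compared with randomising the same clients after the survey. If few clients break off, the loss is small. What then remains is the unstated time at which the arm is revealed. The reading of the order is the natural one, but it rests on narrative and not on a stated position in the survey flow. This is best labelled a cheap improvement.

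**What to change.** Place the Qualtrics randomiser, and the reveal of the arm to client and staff, after the last Connect2Test Assessment and CDE item. The order becomes: consent and HIPAA authorization, full questionnaire, randomisation, then the feedback session (intervention) or the direct offer of testing (control). State this order, and the moment of reveal, in the same words in both Aim 2 descriptions in section C and in section E. If Qualtrics already allocates at that point, only the text needs correcting.

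The cost is a change to the survey flow and a short wording amendment, best made before recruitment, which is expected to last about one month. There are two downsides. More clients must be consented to reach 250 randomised (264 to 313 at the assumed 5 to 20% break-off). The randomised population is also limited to people who complete the survey, which should be stated when the result is generalised.
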